3.4.8.5 Pregnancy

Pregnancies occurring in participants after enrollment must be reported to Sponsor or designee within 72 hours of the site learning of its occurrence. If the participant agrees to submit this information, the pregnancy must be followed to determine the outcome, including spontaneous or voluntary termination, details of the birth, and the presence or absence of any birth defects, congenital abnormalities, or maternal and/or newborn complications. This follow-up should occur even if intended duration of the safety follow-up for the study has ended. Pregnancy report forms will be distributed to the study site to be used for this purpose. The investigator must immediately

(within 24 hours of awareness) report to the Sponsor any pregnancy resulting in an abnormal outcome according to the procedures described for SAEs ([Section 3.4.8.8](#)).

3.4.8.6 Definition and Reporting of Adverse Events Consistent with Anaphylaxis

All suspected cases of anaphylaxis should be recorded as MAAEs and reported as an SAE, based on criteria for medically important event, unless the event meets other serious criteria. As an SAE the event should be reported to the Sponsor or designee immediately and in all circumstances within 24 hours as per [Section 3.4.8.8 Reporting AEs](#). The investigator will submit any updated anaphylaxis case data to the Sponsor within 24 hours of it being available. For reporting purposes, a participant who displays signs/symptoms consistent with anaphylaxis as shown below should be reported as a potential case of anaphylaxis. This is provided as general guidance for investigators and is based on the Brighton Collaboration case definition ([Ruggeberg et al 2007](#)).

Anaphylaxis is an acute hypersensitivity reaction with multi-organ-system involvement that can present as, or rapidly progress to, a severe life-threatening reaction. It may occur following exposure to allergens from a variety of sources.

Anaphylaxis is a clinical syndrome characterized by:

- sudden onset AND
- rapid progression of signs and symptoms AND
- involving two or more organ systems, as follows:

Skin/mucosal: urticaria (hives), generalized erythema, angioedema, generalized pruritus with skin rash, generalized prickle sensation, red and itchy eyes

Cardiovascular: measured hypotension, clinical diagnosis of uncompensated shock, loss of consciousness or decreased level of consciousness, evidence of reduced peripheral circulation

Respiratory: bilateral wheeze (bronchospasm), difficulty breathing, stridor, upper airway swelling (lip, tongue, throat, uvula, or larynx), respiratory distress, persistent dry cough, hoarse voice, sensation of throat closure, sneezing, rhinorrhea

Gastrointestinal: diarrhea, abdominal pain, nausea, vomiting

3.4.8.7 Eliciting and Documenting Adverse Events

The investigator is responsible for ensuring that all AEs and SAEs are recorded in the eCRF and reported to the Sponsor. Unsolicited AEs will be captured from Day 1 through 28 days after each dose up to Day 57 visit in Part A ([Table 9](#)), up to OL-Day 57 visit in Part B ([Table 11](#) and [Table 12](#)), and up to 28 days after the last injection in Part C ([Table 12](#)). Both MAAEs and SAEs will be captured from blinded (Part A) and open-label (Part B) Day 1 throughout entire study duration (Day 394 for Part A, or 6 months post-last vaccination for Part B and C for all participants), as specified in the respective SOEs ([Table 9](#), [Table 11](#), and [Table 12](#)). Any AEs occurring before receipt of the vaccine will be analyzed separately from TEAEs.

At every study site visit or telephone contact, participants will be asked a standard question to elicit any medically-related changes in their well-being according to the scripts provided. Participants will also be asked if they have been hospitalized, had any accidents, used any new medications, changed concomitant medication regimens (both prescription and over-the-counter medications), or had any non-study vaccinations.

In addition to participant observations, data from clinical laboratory test results, physical examination findings, or other documents relevant to participant safety classified as an AE will be documented on the AE page of the eCRF.

3.4.8.8 Reporting Adverse Events

The investigator is responsible for reporting all AEs that are observed or reported during the study, regardless of their relationship to vaccine or their clinical significance. If there is any doubt as to whether a clinical observation is an AE, the event should be reported.

All unsolicited AEs reported or observed during the study will be recorded on the AE page of the eCRF. Information to be collected includes cohort, type of event, time of onset, investigator-specified assessment of severity and relationship to vaccine, time of resolution of the event, seriousness, as well as any required treatment or evaluations, and outcome. The unsolicited AEs resulting from concurrent illnesses, reactions to concurrent illnesses, reactions to concurrent medications, or progression of disease states must also be reported. All AEs will be followed until they are resolved or stable or judged by the investigator to be not clinically significant. The Medical Dictionary for Regulatory Activities (MedDRA) will be used to code all unsolicited AEs.

Any medical condition that is present at the time that the participant is screened but does not deteriorate should not be reported as an unsolicited AE. However, if it deteriorates at any time during the study, it should be recorded as an unsolicited AE.

Any AE considered serious by the investigator or that meets SAE criteria ([Section 3.4.8.3](#)) must be reported to the Sponsor immediately (within 24 hours of becoming aware of the SAE). The investigator will assess whether there is a reasonable possibility that the vaccine caused the SAE. The Sponsor will be responsible for notifying the relevant regulatory authorities of any SAE as outlined in the 21 US CFR Parts 312 and 320. The investigator is responsible for notifying the institutional review board (IRB) directly.

If the eCRF is unavailable at the time of the SAE, the following contact information is to be used for SAE reporting:

- SAE Mailbox: [REDACTED]
- SAE Hotline (USA and Canada): [REDACTED]
- SAE Fax line (USA and Canada): [REDACTED]

3.4.8.9 Assessment of Severity

An event is defined as “serious” when it meets at least one of the predefined outcomes as described in the definition of an SAE ([Section 3.4.8.3](#)), NOT when it is rated as severe.

The severity (or intensity) of an AR or AE refers to the extent to which it affects the participant’s daily activities and will be classified as mild (Grade 1), moderate (Grade 2), severe (Grade 3), or Grade 4 using the following criteria:

- Mild (Grade 1): These events do not interfere with the participant’s daily activities.
- Moderate (Grade 2): These events cause some interference with the participant’s daily activities but do not require medical intervention.
- Severe (Grade 3): These events prevent the participant’s daily activity and require medical intervention.
- Grade 4 (solicited ARs): These events require an emergency room visit or hospitalization.

Changes in the severity of an AE should be documented to allow an assessment of the duration of the event at each level of intensity to be performed. An AE characterized as intermittent requires documentation of onset and duration of each episode.

The Toxicity Grading Scale for Healthy Adult and Adolescent Volunteers Enrolled in Preventive Vaccine Clinical Trials ([DHHS 2007](#)) will be used to categorize local and systemic solicited ARs ([Table 6](#)), clinical laboratory test results, and vital sign measurements observed during this study. Specific criteria for clinical and laboratory abnormalities are presented in [Appendix 2](#) ([Table 13](#) and [Table 14](#), respectively) and will be graded if outside of the reference range for the laboratory utilized.

3.4.8.10 Assessment of Causality

The investigator's assessment of an AE's relationship to vaccine is part of the documentation process but is not a factor in determining what is or is not reported in the study.

The investigator will assess causality (ie, whether there is a reasonable possibility that the vaccine caused the event) for all AEs and SAEs. The relationship will be characterized using the following classification:

- Not related: There is not a reasonable possibility of a relationship to the investigational product. Participant did not receive the investigational product OR temporal sequence of the AE onset relative to administration of the investigational product is not reasonable OR the AE is more likely explained by another cause than the investigational product.
- Related: There is a reasonable possibility of a relationship to the investigational product. There is evidence of exposure to the investigational product. The temporal sequence of the AE onset relative to the administration of the investigational product is reasonable. The AE is more likely explained by the investigational product than by another cause.

3.4.8.11 Follow-up of Adverse Events

All AEs, SAEs, and MAAEs must be reported in detail on the appropriate page of the eCRF and followed until the event is resolved or stable or judged by the investigator to be not clinically significant.

3.4.9 Vital Sign Measurements

Vital sign measurements will include systolic and diastolic blood pressure, heart rate, respiratory rate, and body temperature (preferred route is oral). The participant will be seated for at least 5 minutes before all measurements are taken. Vital signs will be measured at the time points indicated in the Schedule of Events ([Table 9](#), [Table 11](#), and [Table 12](#)). In all parts, blinded and open label, on Day 1 and Day 29 (as applicable), vital sign measurements will be collected once before vaccine administration and at least 30 minutes (Part A) and 30 minutes (Parts B and C) after vaccine administration (before participants are discharged from the study site).

Febrile participants at Day 1 and Day 29 (Parts A, B, and C) visits (fever is defined as a body temperature $\geq 38.0^{\circ}\text{C}/100.4^{\circ}\text{F}$) may be rescheduled within the relevant window periods. Afebrile participants with minor illnesses may be injected at the discretion of the investigator.

When procedures overlap and are scheduled to occur at the same time point, the order of procedures should be vital sign measurements and then the blood collection.

If any of the vital sign measurements meet the toxicity grading criteria for clinical abnormalities ([Table 13](#)) of Grade 3 or greater, the abnormal value and grade will be documented on the AE page of the eCRF (unless there is another known cause of the abnormality that would result in an AE classification). The investigator will continue to monitor the participant with additional assessments until the vital sign value has reached the reference range, returns to the vital sign value at baseline, is considered stable, or until the investigator determines that follow-up is no longer medically necessary.

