4.3 Analysis Endpoints

4.3.1 Part A, Blinded

4.3.1.1 Primary Endpoints

4.3.1.1.1 Primary Safety Endpoints

The primary safety objective will be evaluated by the following safety endpoints:

- Solicited local and systemic ARs through 7 days after each injection.
- Unsolicited AEs through 28 days after each injection.
- MAAEs through the entire study period.
- SAEs throughout the entire study period.
- Safety laboratory abnormalities at Day 29 and Day 57 (Cohort 2 only).
- Vital sign measurements and physical examination findings.

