7. Physical examination: A full physical examination, including height and weight, will be performed at Day 1, Day 29, and Day 57. Symptom-directed physical examinations may be performed at other time points at the discretion of the investigator. On each injection day before injection and again 7 days after injection, the arm receiving the injection should be examined and the associated lymph nodes should be evaluated. Any clinically significant finding identified during a study visit should be reported as an MAAE. Vital signs are to be collected pre- and post-dosing on days of injection (Day 1 and Day 29). When applicable, vital sign measurements should be performed before blood collection. Participants who are febrile (body temperature $\geq 38.0^{\circ}\text{C}/100.4^{\circ}\text{F}$) before injection on Day 1 or Day 29 must be rescheduled within the relevant window period to receive the injection. Afebrile participants with minor illnesses can be administered investigational product at the discretion of the investigator.
8. Pregnancy test at Screening and Day 1 and before the second study injection will be a point-of-care urine test. At the discretion of the investigator a pregnancy test either via blood or point-of-care urine test can be performed. Follicle-stimulating hormone level may be measured to confirm menopausal status at the discretion of the investigator.
9. Sample must be collected prior to dosing on days of injection (Day 1 and Day 29).
10. The nasopharyngeal swab sample, collected prior to vaccination on days of injection (Day 1 and Day 29), will be used to ascertain the presence of SARS-CoV-2 via PCR.
11. Diary entries will be recorded by the participant starting approximately 1 hour after injection while at the study site with instruction provided by study staff. Study participants will continue to record in the eDiary each day after they leave the study site, preferably in the evening and at the same time each day, on the day of injection and for 6 days following injection. Any solicited AR that is ongoing beyond Day 7 will be reported in the eDiary until resolution. Adverse reactions recorded in eDiaries beyond Day 7 should be reviewed either during the next telephone call or at the next study site visit.

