Note: In accordance with “FDA Guidance on Conduct of Clinical Trials of Medical Products during COVID-19 Public Health Emergency” (DHHS 2020), investigators may convert study site visits to telemedicine visits with the approval of the Sponsor.

1. The Participant Decision Visit is only applicable to Part B and may be performed over multiple visits if within the given window.
2. Participants who received 1 dose of mRNA-1273 (50 or 100ug) in Part A and agree to receive 1 dose of mRNA-1273 in Part B, will follow [Table 11](#) Schedule of Events.
3. Safety follow-up via eDiary questionnaire will be performed every 4 weeks starting at OL-Day 71 to OL-Day 155. These study days are relative to OL-Day 1 vaccine administration.
4. Physical examination: A symptom-directed physical examination, including height and weight, will be performed at OL-Day 1, OL-Day 29, and OL-Day 57. Symptom-directed physical examinations may be performed at other time points at the discretion of the investigator. On the day of injection before injection and again 7 days after injection, the arm receiving the injection should be examined and the associated lymph nodes should be evaluated. Any clinically significant finding identified during a study visit should be reported as an MAAE. Vital signs are to be collected pre- and post-dosing on days of injection (OL-Day 1). When applicable, vital sign measurements should be performed before blood collection. Participants who are febrile (body

temperature $\geq 38.0^{\circ}\text{C}/100.4^{\circ}\text{F}$) before injection on OL-Day 1 must be rescheduled within the relevant window period to receive the injection. Afebrile participants with minor illnesses can be administered investigational product at the discretion of the investigator.

5. Sample must be collected prior to dosing on days of injection.
6. The nasopharyngeal swab sample, collected prior to vaccination on days of injection, will be used to ascertain the presence of SARS-CoV-2 via PCR.

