6.1. General Considerations

The Schedule of Assessments is provided in the protocol Table 9 for Part A Blinded Phase, Table 11 and Table 12 for Part B Open-Label Phase.

Continuous variables will be summarized using the following descriptive summary statistics: the number of subjects (n), mean, standard deviation (SD), median, minimum (min), and maximum (max).

Categorical variables will be summarized using counts and percentages.

Baseline value, unless specified otherwise, is defined as the most recent non-missing measurement (scheduled or unscheduled) collected before the first dose of study injection. For safety tests (Part B), the baseline is defined as the non-missing measurement collected on OL-Day 1 and before the first dose of study injection in Part B. For immunogenicity tests (Part A) and nasal swab tests, the baseline is defined as the most recent non-missing measurement (scheduled or unscheduled) collected before or on the date of first dose of study injection (Day 1). For immunogenicity tests (Part B) the baseline is defined as the non-missing measurement collected in Part B and before or on the date of first dose of injection in Part B (OL-Day 1).

For the summary statistics of all numerical variables unless otherwise specified, the display precision will follow programming standards. Please see [Appendix A](#) for variable display standards.

When count data are presented, the percentage will be suppressed when the count is zero in order to draw attention to the non-zero counts. A row denoted “Missing” will be included in count tabulations where specified on the shells to account for dropouts and missing values. The denominator for all percentages will be the number of subjects in that age cohort and vaccination group within the analysis set of interest, unless otherwise specified.

Study day relative to the first injection in Part A will be calculated as below:

- a) study day prior to the first injection will be calculated as: date of assessment/event – date of the first injection in Part A;
- b) study day on or after the date of the first injection in Part A will be calculated as: date of assessment/event – date of the first injection in Part A + 1;

Study day relative to the first injection in Part B will be calculated as below:

- a) study day prior to the first injection in Part B will be calculated as: date of assessment/event – date of the first injection in Part B;

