6.3.4. Vital Sign Measurements

Vital sign measurements, including systolic and diastolic blood pressures, heart rate, respiratory rate, and body temperature, will be presented in a data listing. The values meeting the toxicity grading criteria will be flagged in the data listing. The abnormalities meeting the toxicity grading criteria (Grade 2 or higher) in any vital sign measurement will be listed separately. If a subject has a vital sign result with Grade 2 or higher abnormality at any post injection visit, then all results of vital sign measurement for that subject will be presented in the listing.

Observed values and changes from baseline for all vital sign measurements will be summarized at each visit by age cohort and vaccination group as defined in [Section 6.1](#) for Part A and Part B separately. Shift from baseline in the toxicity grades at each visit and shift from baseline in the toxicity grades to the worst post-baseline result will also be summarized by age cohort and vaccination group for Part A and Part B separately.

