9.2. Appendix B Analysis Visit Windows for Safety and Immunogenicity Analysis

Safety and Immunogenicity Analysis will be summarized using the following analysis visit window for post injection assessments:

Step 1: If the safety and immunogenicity assessments are collected at scheduled visit, i.e. nominal scheduled visit, the data collected at scheduled visit will be used.

Step 2: If the safety and immunogenicity assessments are not collected at the scheduled visit, assessments collected at unscheduled visit will be used using the analysis visit windows described in [Table 4](#) below.

If a subject has multiple assessments within the same analysis visit, the following rule will be used:

- If multiple assessments occur within a given analysis visit, the assessment closest to the target study day will be used.
- If there are 2 or more assessments equal distance to the target study day, the last assessment will be used.

Table 4 Visit Window

Visit	Target Study Day	Visit Window in Study Day
Labs		
Day 29 (Month 1)	29 (Date of Second Injection)	[2, 43]
Day 57 (Month 2)	57	≥44 and prior to Participant Decision Visit

Nasal Swabs for SARS-CoV-2		
Baseline	1 (Date of First Injection)	≤ 1
Day 29 (Month 1)	29 (Date of Second Injection)	[2, 43]
Day 57 (Month 2)	57	[44, 70]
Day 71 or Beyond	71	≥ 71 and prior to Participant Decision Visit
Baseline (OL-Day 1)	1 (Date of First Injection on OL-Day 1) relative to OL-Day 1	≤ 1 and VISIT is OL-Day 1
OL-Day 29	29 (Date of Second Injection in Part B) relative to OL-Day 1	[2, 43]
OL-Day 57	57 relative to OL-Day 1	[44, 70]
OL-Day 71 or Beyond	71 relative to OL-Day 1	≥ 71
Vital Signs		
Day 8	8	[2, 11]
Day 15	15	[12, 22]
Day 29 (Month 1)	29 (Date of Second Injection)	[23, 32]
Day 36	36	[33, 39]
Day 43	43	[40, 50]
Day 57 (Month 2)	57	[51, 133]
Day 209 (Month 7)	209	[134, 301]
Day 394 (Month 13)	394	≥ 302 and prior to Participant Decision Visit
Baseline (OL-Day 1)	1 (Date of First Injection on OL-Day 1) relative to OL-Day 1	≤ 1 and VISIT is OL-Day 1
OL-Day 29	29 (Date of Second Injection in Part B) relative to OL-Day 1	[2, 43]
OL-Day 57 for subjects receiving 2 doses in Part B	57 relative to OL-Day 1	[44, 133]
OL-Day 209 for subjects receiving 2 doses in Part B	209 relative to OL-Day 1	≥ 134
OL-Day 57 for subjects receiving 1 dose in Part B	57 relative to OL-Day 1	[44, 119]

OL-Day 181 for subjects receiving 1 dose in Part B	181 relative to OL-Day 1	≥ 120
Immunogenicity		
Baseline	1 (Date of First Injection)	≤ 1

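### By-visit vital-sign summaries do not separate pre-dose from 30-minute post-dose readings: taken literally, Day 29 shows the post-dose-2 value and the reading after the first dose has no row

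*Protocol*

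**What the plan says.** **Collection.** Protocol 3.4.9 covers all parts and names two injection visits, Day 1 and (where it applies) Day 29. Its rule for these visits reads: "vital sign measurements will be collected once before vaccine administration and at least 30 minutes (Part A) and 30 minutes (Parts B and C". The schedule footnotes agree. Table 9 (Part A) has "Vital signs are to be collected pre- and post-dosing on days of injection (Day 1 and Day 29". Table 11 (Part B, two doses) repeats this for its two injection days. Table 12 (boosters and Part C) has "Vital signs are to be collected pre- and post-dosing on days of injection (OL-Day 1".

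**Endpoint.** "Vital sign measurements and physical examination findings" are listed among the primary safety endpoints for Part A in Protocol 4.3.1.1.1, and the Part B and Part C lists include the same item.

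**Summary.** SAP 6.3.4 (Parts A/B) states: "Observed values and changes from baseline for all vital sign measurements will be summarized at each visit". It adds grade shifts at each visit and a shift to the worst post-baseline result. The Part C SAP has the same plan. Neither mentions a pre-dose or post-dose time point.

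**Selection.** Appendix B first takes data from the nominal scheduled visit and uses windows only where those are missing. For several readings in one analysis visit: "If multiple assessments occur within a given analysis visit, the assessment closest to the target study day will be used". Then: "If there are 2 or more assessments equal distance to the target study day, the last assessment will be used". The Part C SAP has the same two rules.

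**Baseline.** SAP 6.1 (Parts A/B) requires the Part B safety baseline to come from OL-Day 1 before the first Part B dose. The matching vital-sign row in Table 4 limits only study day and visit name. The Part C row in Table 1 adds a pre-dose limit.

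**The concern.** The two readings on an injection day measure different things. The pre-dose reading at Day 29 shows the participant's state about four weeks after dose 1. The post-dose reading shows the immediate response to dose 2. A rule that keeps one of them without regard to dosing puts an acute value in the Day 29 row, between Day 15 and Day 36, as if the three were comparable.

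The first dose has the opposite problem, because there is no row for its acute reading. Under Table 12, a booster or Part C participant has vital signs at OL-Day 1, OL-Day 29, OL-Day 57 and OL-Day 181. The 30-minute reading is thus the only scheduled post-dose one in the first four weeks. By-visit means, changes and grade shifts would not show it, although vital signs are a primary safety endpoint.

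**Working it through.** The plan gives no figure to reproduce, so the check applies Appendix B literally to the scheduled readings.

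**Do same-day readings tie?** In SAP 6.1, "study day on or after the date of the first injection in Part A will be calculated as" assessment date minus first-injection date, plus 1. Clock time does not enter. For a Day 29 visit held on study day d, both readings lie |d − 29| from the target:

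- d = 29: 0 and 0
- d = 36 (end of the +7-day window): 7 and 7
- d = 50 (end of the pandemic +21-day extension): 21 and 21

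The readings tie on every study day from 29 to 50, and the later one, taken after dose 2, is kept. The same holds at OL-Day 29 for two-dose Part B participants.

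**Which readings get a row?** The count starts after the pre-dose baseline reading, with SAP 6.1 governing baseline.

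| Part | Scheduled readings after baseline | By-visit rows | Readings with no row |
|---|---|---|---|
| A | 10: Day 1 post; Days 8, 15; Day 29 pre and post; Days 36, 43, 57, 209, 394 | 8 | Day 1 post; Day 29 pre |
| B, two doses | 5: OL-Day 1 post; OL-Day 29 pre and post; OL-Days 57, 209 | 3 | OL-Day 1 post; OL-Day 29 pre |
| B booster, and C | 4: OL-Day 1 post; OL-Days 29, 57, 181 | 3 | OL-Day 1 post |

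The first post-baseline vital-sign window opens at study day 2 in every part: [2, 11] in Part A and [2, 43] in Parts B and C. A reading 30 minutes after the first dose falls on study day 1 and cannot enter it.

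**How many participants?** Protocol 1.3 reports that 195, 198 and 194 of 200 per arm received the second Part A injection. (195 + 198 + 194)/600 = 587/600 = 97.8%; by arm, 97.5%, 99.0% and 97.0%. This is an upper bound, because it assumes both readings exist for everyone given dose 2. The documents do not give the number of Part B crossovers or boosters. Part C plans about 60.

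**Part B baseline row.** With the window limited only to study day 1 or earlier at the OL-Day 1 visit, both OL-Day 1 readings fit, and the tie rule alone would take the post-dose one. SAP 6.1 says the opposite.

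**The case against.** **Nominal visits come first.** Step 1 of Appendix B uses scheduled-visit data, so the tie rule might be meant only for windowed, unscheduled readings. But both injection-day readings belong to the same nominal visit, and Step 1 does not choose between them. If the tie rule does not apply, no rule does, and the text still needs repair. Table shells, which cannot be seen here, may split the time points; neither SAP says so. That Day 29 shows post-dose values is therefore a literal reading, not a stated intention.

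**The SAP can already tell the readings apart.** For Parts A/B, SAP 6.1 compares date and time with the injection when it derives study day relative to the most recent injection. Table 4 does not use that scale: its Part A targets of 36, 43 and 57 count from dose 1. The rule shows that a split is feasible, but it does not make one.

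**The acute readings are analysed elsewhere.** This stands. A reader might infer that they are lost, and the documents do not support that. All vital signs are listed. A Grade 2 or higher value at a post-injection visit triggers a separate listing of that participant's results. Protocol 3.4.9 sends Grade 3 or higher values to the AE page unless another known cause explains them. A reading after a pre-dose baseline is eligible for the worst-post-baseline shift.

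**A post-dose Part B baseline.** A reader might infer that Part B changes will be measured from a post-dose value. SAP 6.1 defines that baseline explicitly as pre-dose, and a window label should not override it. The gap in Table 4 is a matter of alignment.

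**Placebo participants are injected too.** In Part A, an effect common to any injection would largely cancel between arms. That does not protect within-arm changes, and Parts B and C have no concurrent placebo.

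**Conclusion.** The point holds for by-visit summaries only. On a literal reading, Day 29 in Part A and OL-Day 29 for Part B crossovers report the post-dose-2 reading, for up to 97.8% of Part A participants. The 30-minute reading after the first dose or booster has no by-visit row in any part. The conclusion assumes that Appendix B is programmed as written and that both readings are recorded.

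Two wider inferences are not supported. The documents give no acute effect of injection on any vital sign, so the shift in the Day 29 means cannot be sized, and nothing here shows that a safety conclusion is wrong; the study tests no hypothesis. Nor does the point cover every possible dose. Boosters and Part C receive no injection at OL-Day 29, and neither Protocol 3.4.9 nor the Table 12 footnote specifies pre-dose and post-dose readings for the optional Part C dose at OL-Day 57.

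**What to change.** For the Part B and Part C final analyses, which both SAPs describe as still to come:

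- In Appendix B, apply visit assignment and the tie rule within planned time point (pre-dose, post-dose).
- On injection days, report pre-dose and 30-minute post-dose rows, with the paired change between the two same-day readings.
- Add a pre-dose limit to the Part B vital-sign baseline row of Table 4, as Part C Table 1 already has.

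The Parts A/B SAP (Introduction) says that the Day 57 CSR and the End of Part A addendum are final. Any Part A version should therefore be a supplementary table labelled post hoc.

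The cost is one or two extra table rows per injection visit and some programming. The protocol already schedules both readings, so no new data are needed.
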